characterized. Adverse drug reactions are moderately common in adults, but significantly less in children. Nifurtimox causes gastrointestinal side effects in 50% to 75% of adult patients. These side effects include anorexia, nausea, vomiting, and abdominal discomfort. Mild neurologic toxicity is common (occurring in up to 50% of adult patients), including mainly headache, but also (less commonly) irritability, insomnia, disorientation, mood changes, paresthesias, and tremors. Peripheral neuropathy is a rare side effect in adults. Leukopenia is a very rare side effect [9].

Safety of nifurtimox in the pediatric population is well established. The drug has been used off-label in children for over 40 years. Adverse drug reactions are commonly milder and less frequent than those observed in adults. Studies performed to evaluate the effect of nifurtimox in pediatric oncological disease suggest safety even at super-therapeutic doses (e.g., 30 mg/kg/day) [10]. Case series of pediatric Chagas' patients support the safety of the drug [11].

Consensus documents from the WHO, and the majority of Latin American countries (i.e., Argentina, Brazil, Bolivia) [12][13][14] strongly recommend anti-trypanosomal treatment for acute, congenital, and reactivated *T. cruzi* infection, and for children with chronic infection. Given that Chagas' disease is an infection commonly acquired in childhood that leads to significant morbidity in adults, the benefits of treatment with nifurtimox in infants and children (to prevent long-term complications) far outweigh the small risks of AEs associated with the medication in children.

For the monitoring of efficacy of antitrypanosomal treatment, the criterion of cure usually depends on serologic conversion of anti-*T. cruzi* antibody response to negative. Sero-conversion in children and adolescents may occur several years after treatment, requiring long-term follow-up. Therefore, subjects who were randomized and received at least one dose of their assigned nifurtimox treatment and did not receive additional treatment for Chagas' disease after completion of nifurtimox treatment will be followed up for a total of 4 years after end of nifurtimox treatment.

The overall benefit-risk assessment for the LTFU is considered favorable based on the available data. It is expected that the information will help to gain further knowledge about the serological response after treatment with nifurtimox in Chagas' disease.

4. Study objectives

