A minimum of 38 subjects in each age stratum is targeted, but not required, in order to be able to derive meaningful safety conclusions. Enrollment may⁵³ continue until this specification is met, unless it is determined that such a target would be unlikely to be reached in a reasonable time.⁵⁴

No study-specific procedures will be performed before the subject/legally authorized representative has signed the informed consent form, or a minor subject has provided assent, including asking a potential subject to fast (if applicable, depending on the age of the subject at the discretion of the investigator) prior to the screening blood samples. Informed consent/assent for optional PK blood sampling will also be obtained. After the consents/assents have been obtained, screening assessments will be performed from 1 to 14 days prior to randomization at Visit 2.⁵⁵

After study eligibility has been confirmed and safety assessments have been performed at Visit 2 (Day 1),⁵⁶ subjects will be randomized via Interactive Voice Response System/Interactive Web Response System (IVRS/IWRS) in a 2:1 ratio (60-day regimen vs. 30-day regimen) to one of two treatment groups:

- Nifurtimox tablets administered three times daily for 60 days (Days 1 60, active nifurtimox treatment, Treatment Group 1) or
- Nifurtimox tablets administered three times daily for 30 days, followed by nifurtimox placebo administered three times daily for 30 days (Days 1 30, active nifurtimox treatment; Days 31 60, placebo; Treatment Group 2).

The first dose of study drug will be administered at Visit 2. Pre- and post-dose PK blood samples will be obtained at specified time points from those subjects consenting to PK assessments (see Table 9–1). At the 2 – 4 hour time point of PK blood sampling (i.e., at the time of maximum concentration $[C_{max}]$), an ECG (optional for subjects < 5 years of age at the discretion of the investigator) will be obtained to allow for PK/PD investigations. Study drug

 $^{^{50}}$ Modified as per amendment 2

⁵¹ Text modified for clarity (Amendment 1)

 $^{^{52}}$ Cohort replaced with stratum throughout body of protocol as per amendment 2

⁵³ Text modified as per amendment 4

⁵⁴ Text added as per amendment 2

⁵⁵ Text added for clarity (Amendment 1)

⁵⁶ Text modified for clarity (Amendment 1)

	Integrated Clinical Study Protocol BAY A2502 / 16027	
03 NOV 2020	Version 11.0	Page: 29 of 259

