Also, for reasons of patient safety and at the discretion of the investigator, a subject may be asked to take a "drug holiday" [interruption of study drug administration] or a reduced daily dosage may be requested by the investigator from the depot. A decision by the investigator for drug holiday or reduced dosage will be based on the occurrence and/or severity of adverse effects, and/or the clinical status of the subject. Any and all changes to study drug administration or daily dosage must be recorded within the subject's study chart, as well as, the electronic case report form (eCRF).⁶⁹

Primary variable(s)

The primary efficacy variable will be sero-reduction or sero-conversion at 12 months post-treatment using two conventional ELISA serology tests as the measure of efficacy.⁷⁰

Justification of the design

This study uses an historical untreated-controlled design, as it is unethical to have a prospective placebo-controlled superiority study design. Only two benznidazole placebo-controlled studies have been conducted in children with Chagas' disease.[15][16] Direct comparisons between these studies cannot be made due to differences in study populations (Argentina vs. Brazil), medication dosage (5 mg/kg vs. 7.5 mg/kg), outcome measures, and time of follow-up (4 years vs. 3 years). Data derived from these studies will, however, be used as the comparative historical placebo control to be utilized in the analysis of the study endpoints. Hence, a comparison of sero-reduction and/or sero-conversion from baseline to 12-month follow-up for both primary and secondary endpoint evaluations (versus

⁶⁵ Text deleted/added for clarity (Amendment 1)

⁶⁶ Modified as per amendment 4

⁶⁷ Text modified/deleted for clarity, and per Modifications 9 and 10 (Amendment 1)

⁶⁸ Text added per Modification 11 (Amendment 1)

⁶⁹ Text modified as per amendment 4

⁷⁰ Text modified per Modification 2 (Amendment 1)

	Integrated Clinical Study Protocol	
	BAY A2502 / 16027	
03 NOV 2020	Version 11.0	Page: 31 of 259

historical placebo) will be made as well as for a comparison with benznidazole. Details are presented in Section $10.^{71}$

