9.6.3.3 Physical examination

Part 1 (CHICO)

Physical examinations will be performed by a medically qualified person. A complete physical examination of body systems will be performed at the Screening Visit. A brief physical examination, including assessments of heart, lungs, and abdomen, skin for the presence of severe dermatitis, and assessments for the presence of peripheral neuropathy will be performed at all subsequent designated time points (see Table 9–1). Abnormal findings on physical examination at Screening will be documented as medical history; abnormal findings thereafter will be documented as AEs (see Section 9.6.1.1).¹⁷³

A neurological examination will be performed at Screening, and Visits 3, 6, and 8 (EOT). The examination will include assessments of mental status and cognition, cranial nerves, motor function, deep tendon reflexes, sensation, and coordination and gait. Abnormal findings on neurological examination at Screening will be documented as medical history; abnormal findings thereafter will be documented as AEs (see Section 9.6.1.1).¹⁷⁴

Assessments of Chagas' disease signs and symptoms will be performed at the time of physical examinations (see Section 9.4.4).¹⁷⁵

Part 2 (CHICO SECURE)

Physical examinations will be performed by a medically qualified person. A complete physical examination of body systems will be performed at FU Visit 1, 3, and 5 (see Table 9–2). Abnormal findings on physical examination before signing informed consent will be documented as medical history; abnormal findings thereafter will be documented as AEs (see Section 9.6.1.2). Assessments of Chagas' disease signs and symptoms will be performed at the time of physical examinations.

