## **Adverse Events**

All adverse events occurring during the study (i.e., from signing of informed consent until last visit) will be reported. The MedDRA coding system will be used to code the adverse events.

An overview of frequencies of subjects who died, experienced any adverse event, experienced any drug-related adverse event, experienced a serious adverse event (SAE), experienced a drug-related serious adverse event, or discontinued due to an adverse event will be summarized by treatment regimen.

Adverse events will be considered treatment emergent, if they first occurred or worsened at or after first application of study medication during the course of the study up to and including 7 days after last application of study medication.

Incidence of treatment emergent AEs (TEAEs), drug-related TEAEs, serious TEAEs, drugrelated serious TEAEs, as well as TEAEs leading to discontinuation will be summarized by primary system organ class and high level term by treatment regimen.

The definitions of incidence are as follows:

- Incidence of all events: # of subjects reporting the event with a start date during or after treatment/# of subjects valid for safety.
- Incidence of drug-related events: # of subjects reporting a drug-related event with a start date during or after treatment/# of subjects valid for safety.
- Incidence of events by maximum intensity: # of subjects reporting the event at the indicated intensity with a start date during or after treatment/# of subjects valid for safety.

Adverse events leading to death, premature discontinuation and serious adverse events will be listed. In this study, all AEs of urticarial, weight loss of > 20%, severe rash, and severe polyneuropathy will be considered AEs of special safety interest. Adverse events of special safety interest will be summarized by treatment regimen.

AEs occurring between the time of consent and the first dose of study drug will be summarized separately.

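### Part 1 treatment-emergent AE tables stop at MedDRA high level term, so common non-serious reactions have no assured separate rate by regimen

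*SAP*

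**What the plan says.** The Adverse Events part of SAP 6.3 (Part 1) names five TEAE incidence tables: any, drug-related, serious, drug-related serious, and leading to discontinuation. All five "will be summarized by primary system organ class and high level term by treatment regimen". No lower level is named.

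The same section adds two other kinds of output. The first is listings: "Adverse events leading to death, premature discontinuation and serious adverse events will be listed". The second is a separate by-regimen summary of events of special safety interest, which are urticaria, weight loss above 20%, severe rash and severe polyneuropathy.

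The protocol's benefit-risk assessment (Section 3) describes the known reactions, mainly from adults. On the gastrointestinal side: "These side effects include anorexia, nausea, vomiting, and abdominal discomfort". On the neurological side it names mainly headache, and less commonly "irritability, insomnia, disorientation, mood changes, paresthesias, and tremors". It also says: "Adverse drug reactions are moderately common in adults, but significantly less in children".

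Protocol 5.1 lets the investigator interrupt or reduce dosing. The decision on a "drug holiday or reduced dosage will be based on the occurrence and/or severity of adverse effects", together with the subject's clinical status. Protocol 9.6.3.3 adds a neurological examination at screening and Visits 3, 6 and 8. After screening, "abnormal findings thereafter will be documented as AEs".

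**The concern.** Evaluating safety and tolerability is a secondary objective of Part 1 (SAP 2.1). A high level term is a grouping level, with preferred terms beneath it. If two or more reported reactions fall under one high level term, the table gives the share of subjects with at least one of them and not the rate of each.

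The two regimens are the same for the first month. The shorter one is "Nifurtimox tablets administered three times daily for 30 days, followed by nifurtimox placebo administered three times daily for 30 days", so the arms differ only on Days 31 to 60. The by-regimen TEAE tables are the natural place to see which reactions, if any, become more frequent with the second month of active drug. That question is asked reaction by reaction, and a grouped row may not answer it.

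What is at stake is how much the safety tables can show. Nothing in the efficacy analysis depends on it.

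**Working it through.** The plan states no figure to reproduce, and sample size, power and alpha do not enter. The check sets the relevant places side by side.

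1. **Level that is fixed.** SAP 6.3 fixes system organ class and high level term for all five TEAE tables.

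2. **Is a finer level promised elsewhere?** Four places might do so, and none does.
   - Protocol 10.3.2.1 (Safety) says AEs are summarized by MedDRA terms but gives no level.
   - SAP 4.1 says all collected variables are summarized descriptively, also without a level.
   - SAP 6.3 says all AEs will be reported but not in what form.
   - The SAP 6.3 incidence definitions divide subjects with the event by subjects valid for safety, without tying the event to a term level.

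   The only specific rule is therefore the one in step 1. Finer output is not excluded, but it is not committed to.

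3. **Which tables have a named listing?** The serious, drug-related serious and discontinuation tables do. That leaves 5 - 3 = 2 tables with no listing named: any TEAE and drug-related TEAE.

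4. **Which events rest on those two tables?** Events that are not serious, do not lead to death or discontinuation, and are not of special safety interest. Nausea, vomiting and headache of ordinary severity belong here. So does a reaction that led only to a drug holiday or a lower dose, because the listings do not extend to dose interruption or reduction. Neurological findings after screening are recorded as AEs, so they also enter these tables.

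5. **What does a shared row tell the reader?** Let a row cover reactions with subject-level rates p1, p2, ..., and let r be the share of subjects with at least one. Then

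   max(p1, p2, ...) ≤ r ≤ p1 + p2 + ...

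   Hence each single rate satisfies 0 ≤ p ≤ r, and the row says no more than that. If only one reaction is reported in the row, p = r and nothing is lost.

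6. **How many rows are shared?** This depends on the MedDRA hierarchy and on which events are reported. The documents contain neither, so the number of affected reactions cannot be determined and may be zero.

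**The case against.** The strongest reply is that no loss can be demonstrated. Grouped rows cost information only when reactions share a row, and the documents do not show that any do. That stands, and it limits the point to an assurance the plan does not give.

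A second reply is that finer output remains possible. The wording in protocol 10.3.2.1 and the general reporting statement in SAP 6.3 leave room for it, and the coded data would support it at any time. This also stands: no data are lost. But leaving room is not a commitment, and the one specific sentence stops at high level term.

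A third reply is that the AE tables are not the only route. SAP 6.3 lists physical examination abnormalities as a safety variable separate from AEs. SAP 4.1 has all collected variables summarized at each assessment time by regimen. The examinations in protocol 9.6.3.3 cover mental status and cognition, sensation, coordination and gait, and signs of peripheral neuropathy. White cell counts are in the laboratory panel. A reader might infer that most of the reactions named in the protocol have no by-regimen summary outside the AE tables. The documents do not support that inference, because these routes bear on several of them. No layout is given for the examination findings, however, and this route does not yield a rate for nausea, vomiting or headache.

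Finally, the reactions and frequencies in protocol Section 3 come mainly from adults, and the protocol says reactions are less frequent in children. The list shows the kind of event concerned. It is not a forecast for this trial.

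**Conclusion.** The point holds as a minor one. SAP 6.3 states a coarse reporting level for the Part 1 TEAE tables, and a finer level that uses data already coded is available at almost no cost. Reactions that are non-serious, do not lead to discontinuation and are not of special safety interest have no assured separate rate by regimen wherever they share a high level term. The number affected is unknown and may be none. Where a row is shared, the rate of one reaction is known only to lie between 0 and the row's rate.

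A reader might go further and infer that the tables would conceal a real tolerability difference between the 30-day and 60-day regimens. The documents do not support that. They give no reaction rates by regimen and no information on which reactions share a row or how far they occur in the same subjects. Safety analysis is descriptive, with no formal testing (SAP 6.3, Safety Variables), so no test, decision rule or efficacy conclusion changes.

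The conclusion rests on two things: that the high level term sentence is the operative rule, and the general property of MedDRA that a high level term can group several preferred terms. It concerns Part 1 only, since the Part 2 safety text names no term level.

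**What to change.** In SAP 6.3, Adverse Events, add preferred term as the lowest row, by regimen and overall, in the any-TEAE and drug-related-TEAE tables. Do the same in the serious, drug-related serious and discontinuation tables so that all five share one layout. High level term can stay as an optional intermediate row.

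The cost is one added phrase in the SAP and longer tables. Events are already to be coded in MedDRA, so no new data, visits or coding are needed.

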## Laboratory Data

Quantitative data will be summarized by means of descriptive statistics (arithmetic mean, standard deviation, median, minimum and maximum) by visit and treatment regimen for the original data as well as for the difference to baseline. Frequency tables will be provided for qualitative data. Summaries will be given by treatment regimen. The incidence of laboratory data outside the reference range (low, high) and clinically significant laboratory changes will be summarized by treatment regimen using frequency tables. The definitions of incidence are as follows:

- Incidence of high lab abnormalities: # of subjects with at least one high laboratory assessment after the start of treatment who had a normal or lower than normal laboratory assessment at baseline / # of subjects at baseline with a normal or lower than normal laboratory assessment who also had at least one valid laboratory value after start of treatment. Subjects with missing or high abnormal values at baseline are not included in the denominator.
- Incidence of low lab abnormalities: # of subjects with at least one low laboratory assessment after the start of treatment who had a normal or higher than normal

laboratory assessment at baseline / # of subjects at baseline with a normal or higher than normal laboratory assessment who also had at least one valid laboratory value after start of treatment. Subjects with missing or low abnormal values at baseline are not included in the denominator.

## **ECG and Vital Signs Data**

Quantitative ECG data, both original values and change from baseline, will be summarized by visit and treatment regimen. ECG interpretations will also be summarized by visit and treatment regimen. ECG data will be analyzed for the FAS and by age stratum.

Vital signs data will be analyzed descriptively. The original values and changes from baseline will be summarized by visit and treatment regimen.

#### **Pregnancy Data**

Pregnancy data will be listed by visit and treatment regimen.

## Part 2 (CHICO SECURE)

Safety variables include AEs, physical examination abnormalities, ECG and vital signs. All analyses of safety variables will be descriptive only, no formal testing will be performed.

Adverse events will be recorded when considered at least possibly related to nifurtimox and adverse events caused by protocol-required procedures.

Quantitative ECG data, both original values and change from baseline, will be summarized by visit and treatment regimen. ECG interpretations will also be summarized by visit and treatment regimen. ECG data will be analyzed for the FAS and by age stratum.

Vital signs data will be analyzed descriptively. The original values and changes from baseline will be summarized by visit and treatment regimen.

Pregnancy data will be listed by visit and treatment regimen.

## 6.4 Pharmacokinetics / pharmacodynamics

## Part 1 (CHICO)

Plasma concentration time courses will be analyzed and reported within the study report. In addition, a full PK evaluation of the data will be performed and reported in a separate study

30

report. Population PK methods will be used to provide parameter estimates describing the PK behavior of nifurtimox and to identify possible covariates related to age.

## Part 2 (CHICO SECURE)

Not applicable.

## 6.5 Determination of sample size

## Part 1 (CHICO)

According to Guhl et al. [5], nifurtimox 12 months post-treatment cure rate is about 55%, with a sample size of 260 for the 60-day regimen, the power is 99% for the lower limit of the 95% CI to be greater than 16%.

The number of subjects in the 30-day treatment regimen is based on the width of a 95% CI for the difference of two proportions. A sample size of 130 subjects for the 30-day subjects together with 260 subjects for the 60-day subjects will produce a CI with a width of approximately 20%.

